5.5 Study Drug Accountability

The study pharmacist is unblinded, and will maintain accurate drug accountability records. This log will not be shown to the study Investigators. When the study is completed, copies of the study drug accountability records will be returned to the sponsor, and the originals will be maintained at the study site. Copies of the drug accountability records must be maintained with the rest of the documentation for the study. All unused study drug must be disposed of upon authorization by SAB or its designee. All records regarding the disposition of study drug must be available for inspection by the study monitors and regulatory authorities.

5.6 Concomitant Medications

Subjects will be monitored throughout the study for use of concomitant medications. Any prescription medications, OTC preparations, herbal remedies, and/or nutritional supplements taken during the study period must be recorded in the research record.

5.7 Prohibited Medications

Subjects will refrain from receipt of any investigational drug within 5 half-lives or 30 days, whichever is longer, prior to Day 0 and during the entire study.

6 STUDY PROCEDURES

6.1 Personnel for Study Procedures

The physical examination (excluding vital signs) will be performed by a physician, nurse practitioner, or physician's assistant. All other assessments may be performed by other appropriately trained members of the investigative team as noted on the Delegation of Responsibilities form.

6.2 Screening

Screening evaluations may be done up to 28 days before Day 0.

6.2.1 Informed Consent

The Investigator or designated staff will review informed consent with the subject. One informed consent form will be used for both screening and enrollment into this protocol.

6.2.2 Demographics

The following information should be recorded:

- Age

- Sex
- Ethnicity
- Race

6.2.3 Medical History

The following information should be recorded:

- Medical history including any chronic medical conditions
- Current use of prescription and OTC medications within the last 7 days
- History of allergies
- Current or recent participation in any other research protocols

6.2.4 Clinical Data

- Vital signs (See Section [7.1.3](#))
- 12-lead ECG (See Section [7.3](#))

6.2.5 Physical Exam

A brief physical exam to ensure there are not medical conditions that would increase a subject's risk for participation in this study (Section [7.1.2](#))

6.2.6 Laboratory Testing

The following tests will be performed the day of screening:

- CBC with differential
- Reticulocyte count
- Prothrombin Time (PT) and Partial Thromboplastin Time (PTT)
- Chemistry panel
- Quantitative Immunoglobulins
- Routine urinalysis
- Urine biomarkers
- Serum or urine pregnancy test (females of childbearing potential only)
- Rheumatoid factor

(Elements of each panel are listed in Section [7.1.1](#))

6.2.7 Determination of Eligibility

Once the screening evaluation is complete, eligibility will be determined based on the inclusion and exclusion criteria. Eligible subjects will be contacted, and if still interested in participating, will be scheduled to return to the Clinical Center for randomization and study drug administration. The period of time between screening evaluation visit and administration of study drug should not exceed 28 days.

Subjects that are found to be ineligible will be contacted (or told directly if found ineligible during screening evaluation), and the reason for ineligibility will be discussed. If desired by the subject, and if applicable for the reason for ineligibility, the results will be shared with their

health care provider and/or the subject will be assisted in finding definitive medical care for said condition.

6.3 Detailed Description of Assessments

6.3.1 Schedule of Assessments

The schedule of assessments is described in Table 3. The day when the subject is randomized is denoted as Study Day 0, the first day after enrollment is Study Day 1, etc.

Table 4: Schedule of Assessments

	Screen	Baseline							
Day +/- Window	-28 to -1	-1 to 0	1	2	3 (+1)	7 ± 1	21 ± 2	42 ± 3	90 ± 7
Evaluation/Procedure		Prior to infusion							
ELIGIBILITY									
Informed consent	X								
Demographics	X								
Medical history	X								
RANDOMIZATION/ STUDY DRUG									
Randomize subject		X							
Study drug administration		X							
STUDY PROCEDURES									
Assess Symptoms		X	X	X	X	X	X	X	X
Vital signs	X	X	X	X	X	X	X	X	X
Review of concomitant medications	X	X	X	X	X	X	X	X	X
Physical exam	X	if needed to assess AEs							
ECG	X								
Adverse events		X	X	X	X	X	X	X	X
SAFETY LABORATORY ^a									
CBC	X	X		X	X	X		X	X
PT/PTT	X	X		X	X	X		X	X
Reticulocyte Count	X	X		X	X	X		X	X
Chemistry Panel	X	X		X	X	X		X	
Urinalysis	X	X		X	X	X		X	
Quantitative Immunoglobulin	X	X		X	X	X	X	X	X
Rheumatoid factor	X	X		X	X	X	X	X	X
Urine biomarkers	X	X		X	X	X		X	
Pregnancy test (urine or serum)	X	X							
UDS	X	X							
REFERENCE PROCEDURE									
Stored serum for pharmacokinetics		X ^b	X	X	X	X	X	X	X
Stored serum for immunogenicity ^c			X			X	X	X	X

Notes. a) Elements of each panel are listed in Section 7.1.1

b) PK sample on Day 0 includes baseline (pre-infusion), 1 hour (+/- 15 min) after the end of the infusion, and 6 hours (+/- 30 min) after the end of the infusion.

c) Serum will be collected for immunogenicity assessment for subjects at the time of an AE suggestive of hypersensitivity reaction (including serum sickness) even if the AE does not coincide with a visit in which immunogenicity assessment is planned.

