4.4 Exclusion Criteria

1. Any history of allergy, anaphylaxis, or severe reaction to beef products (including milk and gelatin)
2. Any history of allergy, anaphylaxis, or severe reaction to IVIg or human blood products
3. Any chronic medical problem/condition that require medications needed to maintain the subject's health. Exceptions to this restriction can be allowed for minor health conditions that are treated with Tylenol, over-the-counter non-steroidal anti-inflammatories, vitamins, seasonal allergy medications, or oral/transdermal/IUD contraceptives, etc. The study investigator will make a determination to exclude a subject based upon their medical history and the type and frequency of the drug substance.
4. History of cardiovascular disease, cardiomyopathy, heart failure, or unexplained syncope
5. Abnormal clinically significant 12-lead electrocardiogram (ECG), per PI discretion
6. Subjects who have been laboratory confirmed or clinically diagnosed with influenza within seven days prior to infusion (by subject history) will be deferred from infusion. Any subject with signs and symptoms of an active respiratory infection on the day of infusion will be deferred until the infection is cleared in the opinion of the investigator. Subjects that present with an active upper respiratory infection on the day of infusion will be tested with an FDA licensed Influenza A/B Antigen Test. Signs and symptoms constituting an upper respiratory infection include cough, sore throat, or rhinorrhea with or without fever.
7. Enrollment will be delayed for all patients who have other intercurrent infections (e.g., gastroenteritis, abscess, etc.).
8. Women who are breast-feeding
9. Positive urine or serum pregnancy test
10. Positive urine drug screen (UDS)
11. Clinically significant results, including laboratory results, as determined by study investigator
12. Positive rheumatoid factor
13. IgA deficiency (defined as IgA < 7 mg/dL)

14. Participation in another research study with receipt of any investigational drug within 5 half-lives or 30 days, whichever is longer, prior to study drug administration (i.e., Day 0) and until completion of the study
15. Participation in any other research study until the completion of the study
16. Receipt of blood products within 2 months prior to study drug administration (i.e. Day 0)
17. Receipt of any vaccination within 30 days prior to study drug administration (i.e. Day 0)

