6.3.4.3 Laboratory Testing

The following clinical laboratory tests will be performed and documented:

- CBC with differential
- Reticulocyte Count
- PT/PTT
- Chemistry panel
- Urinalysis
- Urine biomarkers
- Quantitative Immunoglobulins (IgG level)
- Rheumatoid factor
- Serum or urine pregnancy test for women of child-bearing potential
- Stored serum for pharmacokinetics and immunogenicity (16 ml blood)

(Elements of each panel are listed in Section [7.1.1](#))

Only the pregnancy test must be resulted prior to initiation of study drug infusion.

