6.3.7.3 Laboratory Testing

- Stored serum for pharmacokinetics (8 mL blood)

6.3.8 Study Day 2

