7.2 Measures of Pharmacokinetics and Immunogenicity

As noted in the schedule and text above, 8 mL or 16 mL of blood will be obtained for evaluation of pharmacokinetics and immunogenicity. It is anticipated this will be in a serum separator tube (this tube may change without amending the protocol). Serum will be collected for immunogenicity assessment for subjects at the time of an AE suggestive of hypersensitivity reaction (including serum sickness) even if the AE does not coincide with a visit in which immunogenicity assessment is planned.

Pharmacokinetics evaluations will be performed by PPD. As SAB-176 cannot be differentiated from human IgG, the pharmacokinetics evaluations will use Hemagglutination Inhibition assays.

This protocol will evaluate immunogenicity in several assays:

1. anti-IgG antibodies using rheumatoid factor
2. Anti-Drug (anti-SAB-176) Antibody (performed at SAB Biotherapeutics)

7.3 12-Lead ECG

A 12-lead ECG will be obtained according to the Schedule of Assessments.

The ECGs will be measured using an ECG machine that calculates the heart rate and measures PR, QRS, QT, and QTcF.

Subjects will be required to lie quietly in a supine position for at least 5 minutes.

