9.5 Use of Samples/Specimens/Data at the Completion of the Protocol

Samples will be maintained for further laboratory testing for up to 5 years after completion (or closure) of the protocol for the purpose stated in Section 9.1. No long-term storage of samples will occur in this study.

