11.9.2 Secondary Endpoints

- Pharmacokinetic profile of intravenously administered SAB-176 in healthy adults
- Hemagglutination Inhibition (HAI)
- Microneutralization (MN)
- Frequency and concentrations of antibodies caused by SAB-176, as measured by:
 - Anti-IgG antibodies using rheumatoid factor
 - Anti-SAB-176

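### Table 4 puts the first immunogenicity serum on Day 1, the visit text puts it before dosing; if the table is followed, the anti-SAB-176 assay has no designated pre-dose sample

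*Protocol*

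**What the plan says.** Two parts of the Protocol schedule the same sample.

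- **Table 4 (Section 6.3.1).** The row "Stored serum for immunogenicity" has no mark at Screening or Baseline, the latter being the column headed as prior to infusion. It is marked on Days 1, 7, 21, 42 and 90. Note c adds a draw only when an adverse event suggests hypersensitivity.
- **Visit text.** Section 6.3.4 places the baseline evaluation before study drug, and Section 6.3.4.3 lists there "Stored serum for pharmacokinetics and immunogenicity (16 ml blood"). For Day 1, Section 6.3.7.3 lists only "Stored serum for pharmacokinetics (8 mL blood").

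The sample feeds a secondary endpoint in Section 11.9.2: "Frequency and concentrations of antibodies caused by SAB-176, as measured by" rheumatoid factor and anti-SAB-176. Section 7.2 names the anti-drug antibody assay and refers to the schedule and the text together for the blood draws, so it does not say which governs.

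**The concern.** An endpoint worded as antibodies *caused by* the product needs a pre-dose value for each subject. Without one, a positive result on Day 7 or later may reflect either a response to SAB-176 or reactivity that was already there. The protocol gives reason to think prior reactivity is possible. Section 8.1.1 notes that the product may carry alpha-Gal, and that in most subjects who reacted to another alpha-Gal-bearing antibody, IgE was present before treatment. Whether the anti-SAB-176 assay would detect such antibodies is not stated, so this supports relevance but gives no rate.

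The loss would be permanent. This is a single-dose study, so a missed pre-dose draw cannot be repeated after the infusion. A serum taken under note c at a suspected hypersensitivity event would lack the same comparator.

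The rheumatoid factor half is not at risk. It has its own row in Table 4 with Screening and Baseline marks, and "Positive rheumatoid factor" is an exclusion in Section 4.4. Anti-SAB-176 has no screening test and no exclusion.

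**Working it through.** **Immunogenicity serum, visit by visit**

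| Visit | Table 4 | Section 6.3 text |
|---|---|---|
| Baseline (pre-dose) | no | yes |
| Day 1 | yes | no |
| Day 2 | no | no |
| Day 3 | no | no |
| Day 7 | yes | yes |
| Day 21 | yes | yes |
| Day 42 | yes | yes |
| Day 90 | yes | yes |
| Planned draws | 5 | 5 |
| Of which pre-dose | 0 | 1 |

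Only two neighbouring cells disagree and the totals match, as they would if one mark sat a column too far to the right. Six other rows of Table 4 (CBC, PT/PTT, chemistry, quantitative immunoglobulin, rheumatoid factor, PK serum) were compared with the visit text in the same way, and all agree. A column shift in reading the table is therefore unlikely, though the cell should be confirmed on the PDF page.

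**Size of the problem if the table is followed**

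From Table 1, active subjects = 2 + 4 + 6 + 8 = 20 and saline subjects = 1 + 2 + 2 + 2 = 7. The protocol gives no prevalence *q* of pre-existing anti-SAB-176 reactivity, so *q* is assumed over a range.

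- Chance of at least one pre-existing reactor among the active subjects: 1 − (1 − q)^20
- Chance that no saline subject is a pre-existing reactor: (1 − q)^7

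| Assumed q | At least one in 20 active | None in 7 saline |
|---|---|---|
| 1% | 18.2% | 93.2% |
| 2% | 33.2% | 86.8% |
| 5% | 64.2% | 69.8% |
| 10% | 87.8% | 47.8% |

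If all 7 saline subjects are negative, the upper end of the exact two-sided 95% interval for background reactivity is 1 − 0.025^(1/7) = 41.0%. The one-sided 95% limit is 1 − 0.05^(1/7) = 34.8%. On either measure the saline group says little about background, and it cannot show which active subjects were positive before dosing.

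**Other differences between Table 4 and the text**

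| Item | Table 4 | Text |
|---|---|---|
| 6-hour PK sample | ± 30 min (note b) | ± 15 min (Section 6.3.6) |
| Day 21 visit | ± 2 days | ± 1 day (Section 6.3.11) |
| Day 42 visit | ± 3 days | ± 2 days (Section 6.3.12) |

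**The case against.** The best defence is that the text already requires the pre-dose draw, with its own volume, and nothing in Table 4 forbids it. The sample is lost only if a site works from the table and overlooks an explicit instruction. That is fair, and it is why this is a correction to the schedule and not a design fault. But a site may well work from the schedule table, and the protocol does not rank table against text.

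Three fallbacks could be offered if the Baseline draw is missed:

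- **The Day 1 serum in Table 4.** If an induced response is assumed not to appear within about a day of dosing, a Day 1 positive would point to prior reactivity. This has some value, but the sample is taken with drug circulating, which could mask antibody, and the protocol does not state the assay's drug tolerance. It does not reliably replace a pre-dose sample.
- **The pre-infusion PK serum (Table 4, note b).** It is drawn under either version, and Section 9.5 allows retention: "Samples will be maintained for further laboratory testing for up to 5 years after completion". It could perhaps be used, but nothing in the protocol assigns it to the anti-SAB-176 assay.
- **The saline arm.** With 7 subjects it is too small, as shown above.

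It is also true that the prevalence range is assumed, and that the figures give the chance that a reactor exists, not the chance of a wrong conclusion. They should be read as illustration only. The window differences are nested, so a visit or sample inside the narrower text window satisfies both, and no effect on an endpoint has been shown. They matter mainly for deciding what counts as a deviation.

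**Conclusion.** The contradiction is certain on the protocol as read: Table 4 and Sections 6.3.4.3 and 6.3.7.3 disagree at Baseline and Day 1. The harm is conditional. It arises only where a site follows the table, and it is confined to the anti-SAB-176 part of one secondary endpoint. In that case no serum is designated for the assay before dosing, and the available substitutes are weak. How often this would mislead cannot be derived from the protocol. Under assumed prevalences of 1% to 10%, the chance that at least one of the 20 active subjects is a pre-existing reactor is 18% to 88%. The point should be corrected because the missed sample is irrecoverable and the correction is nearly free.

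**What to change.** In Table 4, mark immunogenicity serum in the Baseline (pre-infusion) column, as Section 6.3.4.3 already requires. Then reconcile the Day 1 mark with Section 6.3.7.3, either by removing it from the table or by adding the draw to the text. In the same edit, give one value each for the 6-hour PK, Day 21 and Day 42 windows in Table 4 and in Sections 6.3.6, 6.3.11 and 6.3.12.

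Moving the mark costs no blood. Baseline plus Day 1 stored serum is 16 + 8 = 24 mL under the text, and 8 + 16 = 24 mL under Table 4 if the text's volumes for PK-only and combined draws are applied. Keeping immunogenicity serum at both visits would be 16 + 16 = 32 mL, or 8 mL more per subject.

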6.3.2 Location of Study Drug Administration

The study drug will be administered in the PPD Phase 1 Clinic in Austin, Texas. Subjects will be asked to arrive on the unit at least 60 minutes prior to scheduled time of study drug administration.

6.3.3 Randomization

An order for randomization to SAB-176 or placebo will be entered into CRIS. A blinded treatment allocation is determined by the pharmacy as discussed in Section [5.1](#).

6.3.4 Study Day -1 to Day 0 - Baseline Evaluation

Prior to study drug administration, a baseline evaluation will be performed, including the following:

6.3.4.1 Interval History and Exam

An interval medical history will be performed. This will include:

- Any new medical conditions since screening visit
- Any new medications since screening visit
- Allergies
- Participation in any other research protocols within the last month or since the screening visit, whichever is longer

6.3.4.2 Assessment of Baseline Symptoms

The presence of any baseline symptoms will be elicited and documented.

6.3.4.3 Laboratory Testing

The following clinical laboratory tests will be performed and documented:

- CBC with differential
- Reticulocyte Count
- PT/PTT
- Chemistry panel
- Urinalysis
- Urine biomarkers
- Quantitative Immunoglobulins (IgG level)
- Rheumatoid factor
- Serum or urine pregnancy test for women of child-bearing potential
- Stored serum for pharmacokinetics and immunogenicity (16 ml blood)

(Elements of each panel are listed in Section [7.1.1](#))

Only the pregnancy test must be resulted prior to initiation of study drug infusion.

6.3.5 Study Day 0: Study Drug Administration

SAB-176 or placebo will be prepared as noted in Section [5.3](#). The blinded bag of SAB-176 diluted in sterile normal saline or placebo (sterile normal saline) will be provided to blinded study staff for dose administration.

A peripheral IV will be placed. The dose will be administered as an IV infusion. For each dose, the subject's actual administration time will be recorded in the source documents.

6.3.6 Study Day 0: Peri-Administration Assessments

After study drug administration, subjects will remain in the trial unit for 6 hours after the end of infusion. Monitoring will be performed in a setting with emergency medications, resuscitation equipment and appropriately trained personnel to intervene if needed. The following procedures will occur:

- Vital signs: prior to start of infusion, and then approximately 15 and 30 minutes after the start of the infusion, and every 30 minutes thereafter until the end of the infusion
- Pharmacokinetic Evaluation approximately 1 hour (+/- 15 min) after the end of the infusion. The PK sample (8 ml blood) will be obtained from a separate venipuncture (i.e. not through the infusion IV).
- Vital signs post-dosing will be captured hourly for 6 hours and again at 12h.
- Pharmacokinetic Evaluation approximately 6 hours (+/- 15 min) after the end of the infusion. The PK sample (8 ml blood) will be obtained from a separate venipuncture (i.e. not through the infusion IV).
- Any adverse events occurring during the infusion will be recorded

6.3.7 Study Day 1

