3.2 Study Design

This safety and tolerability study of intravenous (IV) SAB-176 consists of up to 4 single dose-levels or cohorts (cohort 1–4) in a double-blind, randomized, placebo-controlled dose-escalating cohort design. Four cohorts of 2–10 subjects each will be administered a single IV dose of SAB-176 or saline placebo. At very low doses, the concern is primarily allergic or T-cell activation/cytokine storm, so small cohort sizes should be utilized. As the target dose is approached, the sample size will increase to increase the likelihood of detecting toxicity events. The cohorts and dose levels are outlined in [Table 1](#).

Table 1: Cohorts and Dose Levels

Cohort	Number of Subjects Receiving SAB-176				Number of Subjects Receiving Saline Control
	1 mg/kg	10 mg/kg	25 mg/kg	50 mg/kg	
1	2				1
2		4			2
3			6		2
4				8	2

The number of subjects dosed will follow the limitations below:

- The first three subjects of each cohort will be dosed every other day (48-hour interval).
- For Cohorts 2–4, 48 hours after the third subject is dosed, up to 3 subjects may be dosed per day, until the cohort is completed, and no more than 8 subjects will be dosed per week.
- For cohorts 2, 3, and 4, additional dosing in the cohort may continue only after the safety committee recommends continuation after reviewing the safety data from the 3 initial subjects of the cohort.
- After the first three in each cohort, subsequent subjects will be observed for at least 4 hours before beginning the next infusion in the next subject.

Table 2. Example of dosing timeline

	Infusion Day								
	1	2	3	4	5	6	7	8	9
Subject 1	X								
Subject 2			X						
Subject 3					X				
Subject 4							X*		

Table 2. Example of dosing timeline (con't)

	Infusion Day								
	1	2	3	4	5	6	7	8	9
Subject 5							X (≥4 hrs post Subject 4)		
Subject 6							X (≥4 hrs post Subject 5)		
Subject 7								X	
Subject 8								X (≥4 hrs post Subject 7)	
Subject 9								X (≥4 hrs post Subject 8)	
Subject 10									X

* Additional enrollment in the cohort may continue only after the safety committee recommends continuation after reviewing the safety data from the three initial subjects of the cohort.

NOTE: Only 1 subject should be infused at any given time. An infused subject should be observed for at least four hours prior to beginning the next infusion.

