5.3 Dosing and Administration

The NIH clinical center guidelines for administration of a standard human 10% IVIg (10g/100mL) are for the initial rate to be 0.6 mL/kg/hr, and the rate can be increased gradually to a maximum of 4.8 mL/kg/hr, if tolerated.

SAB-176 will be prepared in the following dilutions:

- Cohort 1 will be prepared as a solution 1mg/1ml (0.1% solution by weight), which is 1/100th the concentration of standard human IVIg (e.g. Gammunex).
- Cohort 2 will be prepared as a solution 4mg/1ml (0.4% solution by weight), which is 1/25th the concentration of standard human IVIg.
- Cohorts 3&4 will be prepared as a solution 20mg/1ml (2% solution by weight), which is 1/5th the concentration of standard human IVIg.

The dose of study drug will be calculated based on the subject's dose cohort and weight (up to a maximum weight of 100 kg). The pharmacy will prepare a bag containing the dose of SAB-176 plus as much normal (0.9%) saline as is needed to reach the above listed concentrations. The infusion will be provided in an opaque bag to obscure the bag (as the SAB-176 may develop

bubbles like IVIg if agitated). The drip chamber will also be covered, but accessible if needed by nursing staff for verification of flow rate, etc.

Table 3: Dosing and Administration

Cohort	Dose (mg/kg)	Concentration	Start Rate (mL/kg/hr)	End Rate (mL/kg/hr)	Start Rate (mg/kg/hr)	End Rate (mg/kg/hr)	Proportion of Human IVIG Rate	Duration (mins) (approx.)
1	1	1 mg/mL (0.1%)	0.5	2	0.5	2	1/120 th – 1/240 th	53
2	10	4 mg/mL (0.4 %)	0.5	3	2	12	1/30 th - 1/40 th	85
3	25	20 mg/mL (2 %)	0.5	1	10	20	1/6 th - 1/12 th	83
4	50	20 mg/mL (2 %)	0.5	2	10	40	1/6 th - 1/10 th	97

The infusion will be started at of 0.5 mL/kg/hr, escalating by 0.5 mL/kg/hr increments every 15 minutes to a maximum specified above (end rate).

It is anticipated that the infusion is prepared the morning of the infusion. Since the study drug has been shown stable for 24 hours when mixed in saline, the infusion should be started within 6 hours of preparation in order to assure completion within normal working hours.

The dosing of an individual subject will be slowed and or stopped (depending on clinical assessment) for the following:

- hypotension (systolic or mean blood pressure decreases by 20 mmHg)
- shortness of breath, wheezing, or desaturation
- pain, tenderness, erythema, or swelling around the infusion site
- fevers, chills

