- Other adverse reactions not specified, that are concerning for infusion related adverse events

After clinical assessment, and resolution or improvement of the event of concern, the infusion may be resumed. If the event is not resolving in a reasonable amount of time, the infusion will not be resumed.

However, in order to establish absolute criteria for stopping an infusion – the treatment should be immediately stopped should any of the following occur:

- Profound hypotension (systolic blood pressure < 85 mmHg)
- Shortness of breath, wheezing, or sustained (i.e., ≥ 10 seconds) oxygen saturation < 92% on room air
- Severe (Grade ≥ 3) local infusion site reactions, including pain, tenderness, erythema, or swelling as defined in the protocol-specified toxicity grading scale
- Body core temperature exceeding 38.5°C
- Suspected sepsis
- Severe chest pain
- Suspected anaphylaxis

The subject's actual time of drug administration will be recorded in the source documents.

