7.1.3 Vital Signs, Including SaO₂

At each visit, vital signs assessments (BP, HR, temperature, respiration rate, oxygen saturation).

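### Cohort 1 has no scheduled vital-sign reading at its end infusion rate (45 to 52.5 min); the last one that can still act on the infusion is at about 30 min

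*Protocol*

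**What the plan says.** Protocol section 5.3 starts every infusion at 0.5 mL/kg/hr, "escalating by 0.5 mL/kg/hr increments every 15 minutes to a maximum specified above (end rate". Table 3 gives end rates of 2, 3, 1 and 2 mL/kg/hr for Cohorts 1 to 4, and durations of about 53, 85, 83 and 97 minutes.

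The same section lists findings that slow or stop an infusion. Several need a measurement:
- "hypotension (systolic or mean blood pressure decreases by 20 mmHg" (slow or stop)
- "Profound hypotension (systolic blood pressure < 85 mmHg" (stop at once)
- sustained "oxygen saturation < 92% on room air" (stop at once)
- "Body core temperature exceeding 38.5°C" (stop at once)

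Section 7.1.3 defines the assessment that supplies these values: "vital signs assessments (BP, HR, temperature, respiration rate, oxygen saturation". Section 6.3.6 times it on Day 0: before the infusion, then "approximately 15 and 30 minutes after the start of the infusion, and every 30 minutes thereafter until the end of the infusion", then hourly for 6 hours after dosing and again at 12 hours. No section ties a reading to a rate increase or to reaching the end rate, and none requires continuous monitoring.

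**The concern.** The rate moves on a 15-minute grid, while the readings move to a 30-minute grid after the first half hour. In a short infusion the fastest part can fall wholly between two readings. The numeric limits in section 5.3 then have no scheduled measurement at the highest rate the subject receives.

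Cohort 1 is the first exposure to the product. Section 3.2 says the worry at very low doses is mainly allergy or cytokine release, and section 8.1.1 calls the risks largely unknown. A low protein dose therefore does not remove the reason to measure. At stake is a fall in pressure or a rise in temperature without symptoms, or a fall in saturation if oximetry is not continuous, that meets a section 5.3 limit but is not scheduled to be seen while the infusion can still be changed.

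**Working it through.** **Inputs (section 5.3, Table 3, Table 1).** Dose and concentration: 1 mg/kg at 1 mg/mL, 10 at 4, 25 at 20 and 50 at 20. Start 0.5 mL/kg/hr, plus 0.5 every 15 min, up to the end rate. Subjects: 3, 6, 8 and 10.

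**Formulas.** Volume per kg = dose / concentration. Volume in a full 15-min step = rate × 0.25 h, which at 0.5, 1, 1.5, 2 and 2.5 mL/kg/hr is 0.125, 0.25, 0.375, 0.5 and 0.625 mL/kg. Time at the end rate = remaining volume / end rate.

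**Reproducing the Table 3 durations.**
- Cohort 1: 1 mL/kg. By 45 min, 0.125 + 0.25 + 0.375 = 0.75. The remaining 0.25 at 2 mL/kg/hr takes 7.5 min, so it ends at 52.5 min.
- Cohort 2: 2.5 mL/kg. By 75 min, 0.75 + 0.5 + 0.625 = 1.875. The remaining 0.625 at 3 mL/kg/hr takes 12.5 min, so it ends at 87.5 min.
- Cohort 3: 1.25 mL/kg. By 15 min, 0.125. The remaining 1.125 at 1 mL/kg/hr takes 67.5 min, so it ends at 82.5 min.
- Cohort 4: 2.5 mL/kg. By 45 min, 0.75. The remaining 1.75 at 2 mL/kg/hr takes 52.5 min, so it ends at 97.5 min.

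These agree with the stated 53, 85, 83 and 97 min to within 3%.

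**Overlaying the section 6.3.6 readings.**

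| Cohort | End-rate window (min) | Nominal readings during infusion (min) | Of these, at end rate | Next nominal slot (min) |
|---|---|---|---|---|
| 1 | 45–52.5 | 15, 30 | none | 60 |
| 2 | 75–87.5 | 15, 30, 60 | none | 90 |
| 3 | 15–82.5 | 15, 30, 60 | 30, 60 | 90 |
| 4 | 45–97.5 | 15, 30, 60, 90 | 60, 90 | 120 |

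**Cohort 1, dose after the last reading.** At 30 min, 0.125 + 0.25 = 0.375 mg/kg has been given, so 0.625 mg/kg (62.5%) is left.
- Reading at 25 min: 0.125 + 1 × 10/60 = 0.292 given, 0.708 left.
- Reading at 35 min: 0.375 + 1.5 × 5/60 = 0.50 given, 0.50 left.
- The end-rate step itself is 0.25 mg/kg.

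The final increase, at 45 min, comes after this reading in every case. The step to 1.5 mL/kg/hr is due at 30 min, so it also follows the reading only if the reading is taken first.

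**Cohort 2.** The 90-min slot is 2.5 min after the computed end and 5 min after the stated end. A reading taken 5 min early, at 85 min, lies inside the 75 to 87.5 min window.

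**Scale.** Cohort 1's end rate is 2 mg/kg/hr, which Table 3 gives as Cohort 2's start rate. Cohorts 3 and 4 start at 10 mg/kg/hr and so receive 0.25 mg/kg in 0.25/10 h = 1.5 min.

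**The case against.** The best case against is that nothing here is broken. Section 5.3 acts on symptoms at any minute: breathlessness, wheezing, chills, site reactions, chest pain, suspected anaphylaxis and any other worrying infusion reaction. Section 6.3.6 requires trained staff and resuscitation equipment, and does not forbid extra readings. Section 3.2 says "Only 1 subject should be infused at any given time", so attention is not divided. The saturation limit is worded in seconds, which suggests that oximetry is watched. The Cohort 1 window lasts 7.5 min, in two active and one saline subject, at a rate at which Cohort 2 begins. All of this stands, and it makes the point minor. It does not supply a scheduled blood-pressure or temperature reading at the end rate.

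It could also be said that readings until the end include one at the end. The text does not say so, and such a reading could no longer change the infusion. Nor do approximate times rescue Cohort 1: the 30-min reading would have to be 15 min late, or the 60-min reading more than 7.5 min early. A slowed or interrupted infusion could run into the 60-min slot, but one without incident would not.

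A reader might infer more than the protocol supports:
- *That sections 5.3 and 6.3.6 contradict each other.* They do not. The limits apply whenever a value is known, and no rule links readings to rate steps.
- *That two rate increases always follow the last Cohort 1 reading.* Only one is certain, because the order of step and reading at 30 min is not fixed.
- *That half of the Cohort 2 dose is given without a reading.* The nominal figure after 60 min is (2.5 − 1.25) mL/kg × 4 mg/mL = 5.0 mg/kg, but it rests on a 2.5-min miss of an approximate slot.
- *That every cohort needs a reading at every step.* Cohorts 3 and 4 already have readings at their end rate.

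**Conclusion.** The point holds for Cohort 1: no scheduled reading that can still slow or stop the infusion falls at the end rate, and the last one comes before at least the final rate increase. This assumes that the infusion runs to the section 5.3 steps without interruption. It survives a 5-min shift in the reading times. It also survives the 100 kg dose cap: if the rate follows actual weight, an assumed subject of 110 to 120 kg would finish at 49.8 to 47.5 min, still before the 60-min slot.

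Cohort 2 is borderline and should be described that way. Severity is minor throughout, because the amounts are small and symptom triggers cover most reactions. This is a cheap improvement that makes the protocol's own limits measurable at the highest rate.

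**What to change.** In section 6.3.6 keep all existing times and add one sentence: *In Cohorts 1 and 2, vital signs are also taken immediately before the final rate increase (about 45 min in Cohort 1, about 75 min in Cohort 2) and once within about 5 minutes after the end rate is reached.* Leave the rates and limits in section 5.3, and the schedule for Cohorts 3 and 4, unchanged.

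**Effect.** With the second added reading 3 to 5 min after the final increase:
- Cohort 1 (48 to 50 min): the dose after the last reading is 0.25 − 2 × 3/60 = 0.15 down to 0.25 − 2 × 5/60 = 0.08 mg/kg, against 0.625 now.
- Cohort 2 (78 to 80 min): it is 2.5 − 12 × 3/60 = 1.9 down to 2.5 − 12 × 5/60 = 1.5 mg/kg.

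If the weight cap shortens an infusion so that the second reading would come too late, the reading before the step still applies.

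**Cost.** Two non-invasive readings per subject, 3 × 2 + 6 × 2 = 18 in total, with matching CRF time points. The last step may be delayed slightly while the reading is taken. Only one subject is infused at a time, so the staffing burden is small.
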